19. **Cycle 1:** Serial, 3-mL blood samples will be taken for determination of plasma CPX-POM and metabolites concentrations during Cycle 1 at 0.25, 0.5, 1.0, 1.5, 2.0, 3.0, 4.0, 5.0, 6.0, 8.0, 10.0, 12.0, and 24.0 hours following completion of the 10-minute IV infusion on Day 1 and on Day 5. Each PK sample should be collected as close as possible to the planned time. The 12.0 hour collection can have a +/- 1-hour window (collect within 11 to 13 hours) and the exact time must be recorded. The actual date and time of each blood sample collection will be accurately recorded.
20. **Cycle 1:** Complete 24-hour urine samples for determination of CPX-POM and metabolites concentrations, and measurement of urine volume will be obtained from each patient in urine collection and storage containers during Cycle 1. A sample will be taken at pre-dose on Day 1, and complete urine samples will be collected at 0-12 and 12-24 hour collection intervals post-dose on Days 1 and 5. The 12 hour collection can have a +/- 1-hour window (collect within 11 to 13 hours) and the exact time must be recorded.
21. **Cycle 1:** Urine β -glucuronidase activity will be determined in the complete 24-hour urine samples collected on Day 1 and Day 5 of Cycle 1.
22. 7-mL blood samples will be obtained in EDTA-containing blood collection tubes at pre-dose on Day 1 and Day 5 of each treatment cycle, and on Day 22 of the last treatment cycle. Plasma and buffy coat (PBMCs) will be isolated, transferred to storage tubes, and stored frozen.
23. BSA will be calculated by the site personnel using the Dubois method of calculation using screening height and baseline weight measurements. BSA is to be recalculated before study drug administration on Day 1 of every other treatment cycle, starting with Cycle 3 and the patient's study drug dose adjusted accordingly.
24. CPX-POM infusions will be administered once every 24 hours as 10-minute IV infusions on Days 1-5 of each 21-day treatment cycle. After completion of Cycle 1 for the first 4 to 6 patients, the SRC will review safety, PK, and PD data to determine if any changes to the dosing schedule are indicated (e.g., adding an additional 5 days of dosing to each treatment cycle).

GLOSSARY OF ABBREVIATIONS AND DEFINITION OF TERMS

| | |
|----------------------|---|
| AE | adverse event |
| ALT | alanine aminotransferase |
| ANC | absolute neutrophil count |
| aPTT | activated partial thromboplastin time |
| AST | aspartate aminotransferase |

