Scientists at the University of Kansas synthesized the phosphoryloxymethyl ester of CPX, CPX-POM to enable parenteral administration of CPX. In contrast to CPX and CPX-O, CPX-POM has high water solubility and is readily formulated for parenteral administration.

Pharmacokinetic (PK) studies in laboratory animals showed that CPX-POM is rapidly and completely metabolized to its active metabolite, CPX, which then disappears from plasma following systemic administration of CPX-POM. Following systemic administration of CPX-POM, the dose is eliminated from the body via renal clearance of CPX and the inactive glucuronide metabolite of CPX (CPX-G).

In rats, intravenous (IV) CPX-POM administered for 28 consecutive days did not cause mortality or changes in body weight, food consumption, ophthalmology, hematology, coagulation, clinical chemistry, urinalysis, or organ weights. There were no test item-related findings grossly or microscopically at the highest dose level tested (50 mg/kg/day). Test item-related transient clinical signs, including slight to moderate decreased activity, increased respiration, eating-like behavior, and slight to moderate incoordination were noted immediately after dosing at 50 mg/kg/day. The no observed adverse effect level (NOAEL) in rats was 25 mg/kg/day in males and 50 mg/kg/day in females.

In dogs, CPX-POM administered for 28 consecutive days did not cause mortality or changes in body weight, food consumption, electrocardiogram (ECG) parameters, hematology, coagulation, clinical chemistry, urinalysis, or organ weights. There were no test item-related findings grossly or microscopically at dose levels up to 30 mg/kg/day. Test item-related transient clinical signs such as salivation, fecal changes, aggression, shaking, and tremors were noted after dosing at the highest dose level tested on the study (30 mg/kg/day). Convulsion was apparent in one dog on a single occasion. Test-item related ophthalmic changes were noted in 3/10 dogs treated with 30 mg/kg/day. Thus, the NOAEL in dogs was determined to be 10 mg/kg/day and the highest non-serious toxic dose (HNSTD) in the dog was determined to be 30 mg/kg.

The starting dose of CPX-POM in patients was selected based on the results of the IV CPX-POM 28-day Good Laboratory Practices (GLP) toxicology studies conducted in the rat and dog and consistent with FDA guidance ([FDA, 2010](#)) (see Section 4.4).

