6.1.4. Dosage and Administration

CPX-POM will be administered as an IV infusion once daily on Days 1-5 of each 21-day treatment cycle. CPX-POM will be added to a 100 mL piggyback bag of 0.9% sodium chloride solution and infused over a 10-minute period. The initial dose for the first patient enrolled (i.e., Cohort 1) will be 30 mg/m².

At baseline, the body surface area (BSA) will be calculated by the Dubois method using Screening height and baseline weight measurements. The baseline BSA is to be used to determine the patient's study drug dose. Thereafter, BSA is to be recalculated on Day 1 of every other treatment cycle, starting with Cycle 3, and the patient's study drug dose adjusted accordingly.

$$\text{Dubois Formula: } \text{BSA} = 0.007184 \times W^{0.425} \times H^{0.725}$$

The dose escalation procedure is described in Section 4, and further details and example doses are shown in Section 4.2.

After completion of Cycle 1 for the first 4 to 6 patients, the SRC will review safety, PK, and PD data to determine if any changes to the dosing schedule are indicated (e.g., adding an additional 5 days of dosing to each treatment cycle).

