9.6. Pharmacokinetic Analysis

9.6.1. Pharmacokinetics in Plasma

Plasma concentrations of CPX-POM and its metabolites will be determined by GLP-validated liquid chromatography tandem mass spectroscopy(LC-MS/MS) assays. Analysis of resultant plasma CPX-POM (and its metabolites) concentration-time data will be performed using non-parametric PK data analysis methods using Phoenix WinNonlin 7.0 (Certara LP, Princeton, NJ). PK parameters will be listed and summarized for each analyte using descriptive statistics (e.g., sample size, arithmetic mean, % coefficient of variation, standard deviation, median, minimum, and maximum). The following PK parameters will be determined:

- C_{max} - Maximum observed plasma concentration (C_{max}) observed following administration of a single dose on Day 1
- T_{max} - Time to reach maximum observed plasma concentration (C_{max})
- $AUC_{[0-t]}$ - Area under the concentration-time curve following administration of a single dose on Day 1
- $AUC_{[t-\infty]}$ - Area under the concentration-time curve following administration of a single dose on Day 1 from the last quantifiable concentration (t) to infinity.
- AUC_{inf} - Area under the curve from time zero to extrapolated infinite time [$AUC_{(0-\infty)}$] following administration of a single dose on Day 1 as the sum of $AUC_{[0-t]} + AUC_{(t-\infty)}$
- $C_{SS_{max}}$ - Maximum observed plasma concentration at steady-state on Day 5
- $T_{SS_{max}}$ - Time to reach maximum observed plasma concentration ($C_{SS_{max}}$) on Day 5
- AUC_{SS} - Area under the concentration-time curve over the dosing interval at steady-state following drug administration on Day 5
- λ - Apparent first-order elimination rate constant
- $t_{1/2}$ - Apparent elimination half-life
- Cl_s – Systemic clearance following administration of a single dose on Day 1
- Cl_{ss} – Systemic clearance at steady-state
- V_d – Apparent volume of distribution
- V_{ss} – Steady-state volume of distribution

- C_{max} Derived Accumulation Ratio - C_{SSmax}/C_{max}
- AUC Derived Accumulation Ratio - $AUC_{ss}/AUC_{(0-\infty)}$
- CL_r – Single dose (Day 1) and steady-state (Day 5) renal clearance

Plasma drug and metabolite concentration-time data and derived plasma PK parameters will be presented in tabular and graphic format.

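### With no end-of-infusion plasma sample, prodrug Cmax is biased low, and AUC, clearance and volumes are biased by an amount that depends on an unstated half-life

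*Protocol*

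**What the plan says.** Footnote 19 sets the plasma PK draws "at 0.25, 0.5, 1.0, 1.5, 2.0, 3.0, 4.0, 5.0, 6.0, 8.0, 10.0, 12.0, and 24.0 hours following completion" of the infusion. The same list applies on both PK days, with times counted in "hours following completion of the 10-minute IV infusion on Day 1 and on Day 5". Section 6.1.4 says the drug is "infused over a 10-minute period". The first sample is therefore 15 minutes after the end of infusion and 25 minutes after its start. Section 8.3 refers back to Table 1 and adds no time. In the SAP shells, the plasma listing (16.2.6-2) is only a copy of the urine listing and schedules no further draw.

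The samples are for "determination of plasma CPX-POM and metabolites concentrations during Cycle 1". Section 9.6.1 analyses them by "non-parametric PK data analysis methods using Phoenix WinNonlin 7.0" and lists Cmax, AUC, clearance, Vd and Vss for each analyte. It repeats the peak on Day 5 as "Maximum observed plasma concentration at steady-state on Day 5". The glossary defines Cmax as an observed value. Section 3 makes single- and multiple-dose PK of the prodrug and its metabolites a secondary objective. Section 2 reports from animal studies that "CPX-POM is rapidly and completely metabolized to its active metabolite, CPX". Neither the protocol nor the SAP shells give a prodrug half-life, an assay limit, or a rule for the concentration at time zero.

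**The concern.** After a 10-minute infusion, a drug that is only being lost peaks when the infusion stops. An observed maximum cannot recover a peak that was not sampled. The faster the prodrug disappears, the more of its exposure lies in the unsampled first 25 minutes.

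Cmax, AUC, clearance and both volumes for the prodrug are at stake, on Day 1 and at steady state. There is also a consequence for the QTc work. Footnote 18 and section 8.2.3.5 tie the Holter extractions to the PK draws, so that QTc changes can be related to concentrations taken at the same time. With no draw at the end of infusion, no such pair is planned at the prodrug peak.

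**Working it through.** The plan states no PK figure to reproduce. The check asks what a standard non-compartmental analysis would return on the planned times.

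**Inputs from the protocol.** Infusion time T = 10 min = 1/6 h (section 6.1.4). First sample at t1 = 1/6 + 0.25 = 0.4167 h after the start (footnote 19).

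**Assumptions.** One compartment, dose = V = 1; C(0) = 0 at the start of infusion; linear interpolation while rising and logarithmic while falling; terminal slope known. The half-life is not in the documents, so it is varied.

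**Formulas**, with k = ln 2 / half-life:
- True AUC = 1/k.
- End-of-infusion level: C_end = (1 − e^(−kT)) / (kT).
- First sample: C1 = C_end × e^(−0.25k). The Cmax ratio is therefore e^(−0.25k).
- Computed AUC = ½·t1·C1 + C1/k. Its ratio to truth is C1 × (1 + k·t1/2).
- The clearance ratio is the reciprocal of the AUC ratio. Vss = CL × (AUMC/AUC − T/2).

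**Worked case, half-life 10 min.** k = 4.159 per hour and C_end = 0.5/0.693 = 0.721. The Cmax ratio is e^(−1.040) = 0.354, so C1 = 0.255. The AUC ratio is 0.255 × (1 + 4.159 × 0.2083) = 0.476, and the clearance ratio is 1/0.476 = 2.10.

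**Planned schedule, ratio to truth:**

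| Assumed half-life | Cmax | AUC | CL | Vss |
|---|---|---|---|---|
| 5 min | 0.13 | 0.19 | 5.4 | 17 |
| 10 min | 0.35 | 0.48 | 2.1 | 4.0 |
| 15 min | 0.50 | 0.63 | 1.6 | 2.5 |
| 30 min | 0.71 | 0.81 | 1.23 | 1.52 |
| 60 min | 0.84 | 0.91 | 1.10 | 1.22 |
| 120 min | 0.92 | 0.96 | 1.05 | 1.10 |

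A volume calculated as CL/k carries the same ratio as CL. Linear interpolation throughout gives AUC ratios of 0.21, 0.52, 0.67, 0.84, 0.925 and 0.98, so the missing sample, not the trapezoid rule, drives the result. If the assay limit were 0.1% of the end-of-infusion level (an assumption), a 5-minute half-life would leave only two quantifiable samples. The terminal slope, and with it AUC to infinity, clearance and volume, might then not be estimable.

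**With one end-of-infusion sample added.** Cmax is exact in this model. The AUC ratio becomes C_end × (1 + kT/2): 0.92, 0.97, 0.99, 1.00 and 1.00 at 5, 10, 15, 30 and 60 min (1.105 falling to 1.016 with linear interpolation throughout). Vss is still 1.40 times true at 5 min, 1.12 at 10 min and 1.02 at 30 min.

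**Day 5 pre-dose sample.** The schedule has none. Setting the pre-dose value to zero removes an area of ½ × t1 × trough. At a 4-hour half-life the trough is 1.6% of the end-of-infusion level, or about 0.016. The area lost is 0.5 × 0.4167 × 0.016 = 0.0034, against a true 1/k of 5.77, which is 0.06%. Up to 2 hours it is below 0.002%; even at 12 hours it is 0.4%.

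**The case against.** Five points can be made against the concern.

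- **The half-life is unknown, and the description of fast conversion comes from animals.** This stands. At 2 hours the errors are about 10% or less. A reader might infer that the prodrug parameters will simply be wrong; the documents support only a bias of unknown size. The direction of the Cmax bias needs only that the prodrug falls after infusion. The AUC, clearance and volume figures also depend on the time-zero rule.
- **The active species is CPX, not the prodrug.** This stands. On the planned times, with assumed prodrug half-lives of 2 to 30 minutes and CPX half-lives of 1 to 8 hours, CPX Cmax and AUC were 94–100% of true, and at least 97% once the prodrug half-life was 5 minutes or more. CPX-G forms later still. The accumulation ratios are largely preserved because both days share the same gap.
- **The missing Day 5 pre-dose sample.** A reader might infer that this also distorts prodrug steady-state AUC. It does not: the effect is 0.06% or less up to a 4-hour half-life. Footnote 24 says "CPX-POM infusions will be administered once every 24 hours as 10-minute IV infusions on Days 1-5", so with no Day 6 dose the 24-hour sample can stand in for the trough. That substitution would fail if the Safety Review Committee extended dosing. What is lost is a pre-dose check of metabolite steady state.
- **The ECG at the peak is not lost.** This is correct: the Holter recording is continuous and could be re-extracted. Only the paired concentration would be missing.
- **Dose escalation rests on toxicity.** This is also correct. Section 9.5.1 defines the MTD by DLT counts. PK does enter the committee's schedule review after the first 4 to 6 patients (section 9.8), but nothing ties that review to prodrug clearance.

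**Conclusion.** The concern holds for the end-of-infusion gap. If the prodrug declines after infusion, its observed Cmax and CSSmax are biased low; with C(0) = 0, AUC is also biased low and clearance and volumes high. The size runs from several-fold at half-lives of 5 to 10 minutes to about 10% or less at 2 hours. These figures rest on a one-compartment model, an assumed half-life and an assumed time-zero rule. A fast distribution phase would make the missed part larger. The animal description points towards the short end without fixing a value.

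The finding affects the prodrug part of a secondary objective and the planned QTc–concentration pairs. It does not reach the MTD, and it does not undermine the PK of CPX or CPX-G. A change is worth making because it is cheap and the possible bias is large.

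**What to change.** Add an end-of-infusion plasma sample to footnote 19 on Day 1 and Day 5, and on Day 5 of Cycle 2 where steady-state sampling is postponed. Add the matching extraction to footnote 18 for the day the Holter is worn. Keep all existing times: dropping middle draws such as 5 h and 10 h would take points from the metabolite profiles and remove the Holter extractions tied to them.

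State in section 9.6.1 or the SAP the time-zero value, the interpolation rule and the minimum number of points for the terminal slope. If the half-life proves to be about 5 minutes, report prodrug Vss with caution, since it would still be about 1.4-fold high.

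Optionally, draw a Day 5 pre-dose PK sample with the pre-dose biomarker blood already planned in footnote 22, solely to check metabolite steady state.

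The cost is one extra 3-mL draw per PK day, or two on Day 5 with the optional sample: 6 to 9 mL over both days. Section 8.3 already requires PK samples to come from a site other than the infusion site.

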2. INTRODUCTION

CPX-POM is a prodrug of ciclopirox (CPX). CPX is a synthetic antifungal agent approved for topical dermatologic use in the treatment of a broad spectrum of fungal organisms (Gupta, 2001). CPX and ciclopirox olamine (CPX-O) are contained in a number of marketed topical drug products. CPX also exerts antibacterial activity against many Gram-positive and Gram-negative bacteria (Abrams et al, 1991). CPX is a hydroxypyridone that is structurally unrelated to other antifungal agents and has a unique and complex mode of action. CPX is thought to act through the chelation of polyvalent metal cations, such as iron and aluminum, resulting in the inhibition of the metal-dependent enzyme systems (e.g., cytochromes, catalase, peroxidase), thus disrupting cellular activities, such as inhibiting degradation of peroxides within the fungal cells (Gupta and Plott, 2004) and mitochondrial electron transport processes and energy production (Sakurai et al, 1978; Gupta et al, 1994). It is also thought that CPX affects the cytoplasmic membranes, inhibiting transport of essential elements in the fungal cell, disrupting the synthesis of DNA, ribonucleic acid (RNA), and protein (Gupta and Plott, 2004). In addition, CPX may have anti-inflammatory activity as demonstrated by its ability to inhibit the synthesis of prostaglandins and leukotrienes in human polymorphonuclear cells (Abrams et al, 1991) and to inhibit the formation of 5-lipoxygenase and ciclo-oxygenase (Bohn and Kraemer, 2000; Hanel et al, 1991).

CPX has demonstrated in vivo and/or in vitro anticancer activity in at least 17 types of solid tumor and hematologic cancers (CPX-POM Investigators Brochure, 2017). CPX modulates iron-dependent enzymes and signaling pathways resulting in inhibition of cell growth, proliferation, and survival. CPX has been demonstrated to chelate intracellular iron in human cancer cells (Kwong et al, 2015; Eberhard et al, 2009; Sidarovich et al, 2015), which plays an important role in cancer cell death resulting from exposure to CPX (Clement et al, 2002; Szüts and Krude, 2004; Eberhard et al, 2009; Sidarovich et al, 2015). CPX exposure altered expression of 54 proteins in stem cells, including those associated with nucleotide binding, biosynthetic processes, gene expression, regulation of transcription, cell cycle processes, RNA and messenger RNA (mRNA) processing, and embryonic development (Dihazi et al, 2011).

Scientists at the University of Kansas synthesized the phosphoryloxymethyl ester of CPX, CPX-POM to enable parenteral administration of CPX. In contrast to CPX and CPX-O, CPX-POM has high water solubility and is readily formulated for parenteral administration.

Pharmacokinetic (PK) studies in laboratory animals showed that CPX-POM is rapidly and completely metabolized to its active metabolite, CPX, which then disappears from plasma following systemic administration of CPX-POM. Following systemic administration of CPX-POM, the dose is eliminated from the body via renal clearance of CPX and the inactive glucuronide metabolite of CPX (CPX-G).

In rats, intravenous (IV) CPX-POM administered for 28 consecutive days did not cause mortality or changes in body weight, food consumption, ophthalmology, hematology, coagulation, clinical chemistry, urinalysis, or organ weights. There were no test item-related findings grossly or microscopically at the highest dose level tested (50 mg/kg/day). Test item-related transient clinical signs, including slight to moderate decreased activity, increased respiration, eating-like behavior, and slight to moderate incoordination were noted immediately after dosing at 50 mg/kg/day. The no observed adverse effect level (NOAEL) in rats was 25 mg/kg/day in males and 50 mg/kg/day in females.

In dogs, CPX-POM administered for 28 consecutive days did not cause mortality or changes in body weight, food consumption, electrocardiogram (ECG) parameters, hematology, coagulation, clinical chemistry, urinalysis, or organ weights. There were no test item-related findings grossly or microscopically at dose levels up to 30 mg/kg/day. Test item-related transient clinical signs such as salivation, fecal changes, aggression, shaking, and tremors were noted after dosing at the highest dose level tested on the study (30 mg/kg/day). Convulsion was apparent in one dog on a single occasion. Test-item related ophthalmic changes were noted in 3/10 dogs treated with 30 mg/kg/day. Thus, the NOAEL in dogs was determined to be 10 mg/kg/day and the highest non-serious toxic dose (HNSTD) in the dog was determined to be 30 mg/kg.

The starting dose of CPX-POM in patients was selected based on the results of the IV CPX-POM 28-day Good Laboratory Practices (GLP) toxicology studies conducted in the rat and dog and consistent with FDA guidance ([FDA, 2010](#)) (see Section 4.4).

CicloMed is aware of 2 published reports of CPX-O administered orally to humans ([Minden et al, 2014](#); [Kellner et al, 1981](#)). Following oral administration of CPX-O to patients with refractory hematologic malignancies, evidence of pharmacodynamic (PD) activity was observed ([Minden et al, 2014](#); [Song et al, 2011](#)). Administration by the oral route of administration, however, is not feasible because of dose-limiting gastrointestinal toxicity and poor oral bioavailability due to high first pass effect ([Minden et al, 2014](#)).

The Investigator's Brochure provides further details of the nonclinical studies and published clinical evaluations of CPX-POM ([CPX-POM Investigator's Brochure, 2017](#)).

3. OBJECTIVES

The primary objective of this study is:

- To evaluate the dose limiting toxicities (DLTs) and maximum tolerated dose (MTD) of CPX-POM administered IV and establish the CPX-POM dose recommended for further investigation.

The secondary objectives of this study are:

- To characterize the plasma and urine PK of CPX-POM and its metabolites following single and multiple dose administration;
- To identify preliminary anti-tumor activity of CPX-POM;
- To determine urine β -glucuronidase activity in patients participating in the trial.

The exploratory objectives of this study are:

- To characterize the pharmacologic effects of CPX-POM on circulating biomarkers of Wnt and Notch cell signaling pathways;
- To explore PD relationships between changes in circulating biomarkers and drug and/or metabolites exposure and other outcomes.

4. STUDY DESIGN

4.1. Overall Design

This is a first-in-human, Phase 1, multicenter, open label, dose escalation study to evaluate the DLTs and MTD and to determine the recommended Phase 2 dose (RP2D) of CPX-POM administered IV in patients with any histologically- or cytologically-confirmed solid tumor type. Secondary objectives include characterization of the safety and PK profile of CPX-POM and identification of preliminary anti-tumor activity in this patient population. Biomarkers and their relationship to PK and other outcomes will be examined as an exploratory objective.

The study will initially employ an accelerated titration design, with a single patient enrolled in each cohort (i.e., Single-Patient Cohorts). The initial patient cohort will receive CPX-POM at a starting dose of 30 mg/m². Doses will be escalated in 100% increments (i.e., doubling), until a \geq Grade 2 toxicity (with the exception of alopecia), as determined according to the United States (US) National Cancer Institute (NCI) Common Terminology Criteria for Adverse Events (CTCAE), version 4.03, is encountered, at which point that cohort and all subsequent cohorts will follow a classical “3 + 3” dose escalation design (i.e., standard cohorts).

After each cohort is completed, a Safety Review Committee (SRC) comprised of the CRO Medical Monitor, Principal Investigator(s), and Sponsor representatives will meet to discuss the data and decide upon the next dose escalation. Doses in the standard cohorts will be escalated in 25 to 50% increments, based on SRC decision, until the MTD is reached. In addition, after completion of Cycle 1 for the first 4 to 6 patients, the SRC will review safety, PK, and PD data to determine if any changes to the dosing schedule are indicated.

Inpatient dose escalation will not be allowed in any patient at any time.

Each patient in a dose cohort must have received at least 80% of their CPX-POM doses, unless due to toxicity, during Cycle 1 with follow-up safety evaluations through Day 22 (or Cycle 2, Day 1, if continuing in the study) to be eligible for the assessment of DLT.

Patients may continue to receive cycles of CPX-POM until progression of disease, intolerable toxicity occurs, or another withdrawal criterion applies.

Approximately 24 patients will be enrolled in the Single-Patient and Standard Dose Escalation Cohorts to establish the MTD. In addition to these estimated 24 patients, Expansion Cohort(s) may be enrolled after the MTD is reached to either explore different dosing schedules, increase the experience with a particular tumor type (e.g., muscle invasive

bladder cancer [MIBC]), or to examine the safety and anti-tumor activity of CPX-POM in combination with certain other anticancer agents.

All patients are to attend a Follow-up Visit 28 days (\pm 5 days) after the last study drug dose. No follow-up after completion of the Follow-up Visit is planned, with the exception of monitoring of ongoing treatment-emergent adverse events (AEs) until resolution or until the AE is clearly determined to be due to a patient's stable or chronic condition or intercurrent illness(es).

Dose escalation procedures will be conducted as shown in Table 2. For further details and example doses, see Section 4.2.

Table 2. Dose Escalation Procedures

| Accelerated Titration (Single-Patient Cohorts; n=1 each) | |
|---|---|
| No \geq Grade 2 AEs | 
 Continue evaluation of single-patient dose cohorts. Escalate by 100% to next dose level. |
| At least 1 \geq Grade 2 AE not meeting the definition of DLT | 
 Expand current and subsequent cohorts to at least 3 patients (see Standard Dose Escalation Scheme below). |
| 1 DLT | 
 Expand current cohort up to 6 patients or until 2 DLTs are encountered (Standard Dose Escalation Scheme below). |
| Standard Dose Escalation (Standard Cohorts; n=3 to 6 each) | |
| No DLT | 
 Escalate by 25–50% to next dose level. |
| 1 DLT in \leq 3 patients | 
 Expand cohort up to 6 patients. |
| 1 DLT in 6 patients | 
 Escalate by 25–50% to next dose level. |
| > 1 DLT in \leq 6 patients | 
 MTD reached; stop dose escalation. Possibly explore intermediate doses for the RP2D. |

Abbreviations: AE = adverse event; DLT = dose limiting toxicity; MTD = maximum tolerated dose; RP2D = recommended Phase 2 dose.

A Dose-Limiting Toxicity will be defined as any of the following, if deemed related to study drug:

- Grade 4 thrombocytopenia of any duration
- Grade 3 thrombocytopenia with significant hemorrhage of any duration
- Grade 4 absolute neutrophil count (ANC) greater than 5 days
- Febrile neutropenia
- Grade ≥ 3 non-hematologic toxicity of any duration, except:
 - Grade 3 nausea, vomiting, or diarrhea and Grade 4 vomiting or diarrhea in the absence of maximal medical therapy that resolves in 72 hours
 - Grade 3 fatigue lasting < 5 days
 - Grade 3 hypertension that can be controlled with medical therapy
 - An increase of indirect (unconjugated) bilirubin indicative of M. Meulengracht/Gilbert's syndrome
 - Serum lipase and/or serum amylase CTCAE Grade 3 ≤ 7 consecutive days without clinical signs or symptoms of pancreatitis
- Delay in study drug due to toxicity for > 2 weeks
- alanine aminotransferase (ALT)/aspartate aminotransferase (AST) $> 3x$ the upper limit of normal (ULN) with bilirubin $> 2x$ ULN without another explanation (e.g., cholestasis)
- Any patient who is unable to receive 80% of the expected doses of CPX-POM (i.e., patients who are unable to receive at least 4 of the 5 scheduled doses) in Cycle 1 because of AEs will be considered to have a DLT.

